5 STUDY DRUGS

All study drug supplied by the Sponsor must be stored in a secure location accessible only to designated study personnel.

5.1 Description of Study Drug

Telavancin drug substance is manufactured as telavancin hydrochloride and is marketed as VIBATIV®. Telavancin hydrochloride is a lipoglycopeptide antibacterial that is a synthetic derivative of vancomycin. Telavancin is supplied in single-use vials containing 750 mg telavancin as a sterile, preservative-free lyophilized powder. Inactive ingredients are hydroxypropylbetadex, mannitol, and sodium hydroxide and hydrochloric acid used in minimal quantities for pH adjustment.

Telavancin is to be stored at refrigerated temperatures of 2°C to 8°C (35°F to 46°F). Excursions to room temperatures (up to 25°C [77°F]) for up to 7 days are acceptable.

Refer to the telavancin pharmacy manual for details on handling, reconstitution, dilution, and administration.

5.2 Dosage and Administration

Telavancin will be administered by qualified study site personnel as a single IV infusion using an IV pump over approximately 60 minutes. Telavancin may be administered without regard to meals. The first eight (8) subjects will receive a single dose of telavancin (10 mg/kg). The appropriateness of the 10 mg/kg dose will be evaluated after completion of a total of approximately 8, 16, 24, and 30 subjects in Cohorts 1- 4 using PK methods as described in Section 3.1.

The start time, stop time, and rate of each infusion will be recorded in the source documents for all subjects. Should red man syndrome (Section 1.4.1) occur in association with the infusion, the infusion should be stopped and not resumed. If the infusion is stopped for any reason, the following must be recorded in the source documents: the reason for stopping the infusion, the stop time of the infusion, and the rate of infusion just prior to being stopped. These data will be used to calculate the total amount of telavancin infused into the subject. All remaining study procedures should be completed for the subject.

5.3 Treatment Compliance

Subjects will receive a single IV dose of telavancin administered by qualified study personnel at the study site. Compliance with the dosing regimen will be assessed by reconciliation of used and unused study drug. Any discrepancies will be reviewed with the site staff and retraining on proper dosing will occur as needed.

5.4 Drug Accountability and Reconciliation

The investigator or designee is responsible for maintaining accountability records for all study drug(s) received from the Sponsor, in accordance with applicable government regulations and study procedures. The accountability records for study medication (telavancin) will be maintained in a secure location, accessible only to authorized staff members. The accountability record will include entries for receipt, distribution or dispensing, and destruction of the material(s).

Unused and expired study drugs will be disposed of in accordance with written instructions from the Sponsor. Copies of the study medication accountability records will be provided to the Sponsor at completion of the study and will be made available for review by the site monitor during the course of the study.

6 STUDY PROCEDURES

6.1 Schedule of Study Procedures

The schedule of study procedures is summarized in Table 1 and Table 2.

6.2 Total Blood Volume

The total volume of blood to be drawn from each subject for PK and safety laboratory assessments is approximately 15 mL for females who are post menarche and 14.0 mL for males and pre-menarchal females as outlined in Appendix 7. Additional safety laboratory tests may be drawn, as required for safety assessments. Exact volumes will depend on individual sample volumes required at each institution. Blood sample volume must not exceed 5% of total blood volume (TBV) over 24 hours and up to 10% of TBV over 8 weeks. The investigator must ensure that the total volume of blood drawn does not exceed 5% of total blood volume especially in the youngest cohort. References for safe limits for a maximum blood volume to be drawn can be found in Appendix 8.

6.3 Procedures by Visit

Written assent, if applicable, and written informed consent must be obtained before any protocol specific procedures are performed.

The site should make every effort to perform procedures at the scheduled times, and the actual time should be recorded in the source documents and case report forms. When multiple assessments are scheduled at the same nominal time, PK sample collections should occur as close as possible to the scheduled nominal time. ECGs and vital signs may be collected prior to the PK sample collection.

6.3.1 Screening

The screening visit will be performed within 48 hours before planned dosing. Screening activities will comprise the following:

- Written, signed, and dated informed consent must be obtained after the nature of the study has been explained to the legally authorized representative and subject, if applicable, and before any study procedures are performed. Where applicable, assent will also be obtained based on local IRB requirements.
 - Review of inclusion and exclusion criteria (Subjects will be eligible for enrollment only if they meet all the inclusion and none of the exclusion criteria)
 - Medication and medical history
-

- Height and weight
- Vital signs
 - Heart rate (HR) and blood pressure (BP)
 - Respiratory Rate (RR) and body temperature
- ECG (12-lead)
- Physical examination as outlined in Section 6.4.3.4
- Blood collection (NOTE: If standard clinical laboratory tests have been performed within the protocol-specified windows for laboratory testing at screening, the results may be used to avoid excessive blood draws.)
 - Hematology
 - Serum chemistry
 - Serum pregnancy test (for females who are post menarche)
- Urine collection for urinalysis
- Concomitant medications
- Adverse events

6.3.2 Day 1 (see Table 1)

The following procedures will be performed on Day 1:

Pre-Dose Procedures:

- Review of inclusion and exclusion criteria (Subjects will be eligible for enrollment only if they meet all the inclusion and none of the exclusion criteria)
- Vital signs
 - HR and BP
 - RR and body temperature
- ECG (12-lead), (if not done within the past 24 hours)

Dosing:

- Study medication (telavancin) dosing, IV over 60 minutes (\pm 5 minutes)
-

Post dose Procedures:

- Vital signs at 1 (\pm 20 minutes) and 4 hours (\pm 20 minutes) after the start of the telavancin infusion
 - HR and BP
 - RR and body temperature
- ECG (12-lead), to be recorded between 1.5 and 2.5 hours (\pm 10 minutes) after the start of the telavancin infusion
- Blood collection
 - PK samples will be collected at 1 hour (\pm 5 min), 1.5 hours (\pm 5 min), 2 hours (\pm 5 min), 6 hours (\pm 30 min), and 12 hours (\pm 30 min), after the start of the telavancin infusion
- Adverse events
- Concomitant medications

6.3.3 Day 2 (Day of Discharge)

The following procedures will be performed on Day 2:

- Vital signs at 24 hours (\pm 2 hours) after the start of the telavancin infusion
 - HR and BP at 24 hours (\pm 2 hours) after the start of the telavancin infusion
 - RR and body temperature
- Blood collection
 - PK samples will be collected at 24 hours (\pm 30 minutes) after the start of the telavancin infusion
 - Hematology and serum chemistry laboratory testing. (NOTE: If standard clinical laboratory tests have been performed within the protocol-specified windows for laboratory testing on Day 2 (same calendar day), the results may be used to avoid excessive blood draws.)
 - Adverse events
- Concomitant medications

6.3.4 Day 8 (\pm 1 day)/Follow-Up

The following procedures will be performed at the Follow-Up (Day 8 \pm 1 day), which should occur 7 days after dosing. At the discretion of the Investigator, the Follow-Up Visit may be either a clinic visit or telephone call:

- Adverse events
 - Concomitant medications
-

6.3.5 Study Termination

Study termination will be considered the date that the subject withdraws from or completes the study, even if that date does not correspond to a protocol-specific visit.

6.3.6 Pregnancy Reporting

Study participants should be advised to inform the study physician immediately if they become pregnant, or their partner becomes pregnant, while participating in the study (Section 1.4.2).

6.4 Description of Study Assessments

6.4.1 Demographic and Baseline Assessments

6.4.1.1 Demographic Information

Demographic information to be collected will include: date of birth, sex, race, and ethnicity.

6.4.1.2 Height and Weight Measurements

Height and weight will be measured and recorded as outlined in Table 1. The subject's weight must be within the 3rd and 97th percentile (inclusive) for age and sex. For subjects aged > 12 months to <24 months, the charts in Appendix 1 and Appendix 2 should be used. For subjects age 2 to 17 years, Appendix 3 and Appendix 4 should be used.

Height or length (in centimeters) and weight (in kilograms) should be measured with the subject's shoes off. The body weight from Screening will be used to calculate the telavancin dose.

6.4.2 Pharmacokinetic Assessments

Blood samples for plasma PK assessments will be collected and processed according to instructions specified in the Pharmacokinetic Sample Collection Manual separate from this document. The total blood volume for PK is discussed in Section 6.2 and is outlined in Appendix 7.

Blood samples for PK assessment will be collected as follows:

- After the start of infusion: 1.0 hour (± 5 min), 1.5 hours (± 5 min), 2 hours (± 5 min), 6 hours (± 30 min), 12 hours (± 30 min), and 24 hours (± 30 minutes after the beginning of the telavancin infusion).
-

The actual time of collection must be recorded for each sample. Note that the PK sampling scheme may be optimized after the completion of each interim analysis to assure that the minimum number of samples are used in each subsequent set of six or eight subjects.

Refer to the Pharmacokinetic Sample Collection Manual for specific information on the collection and processing of PK plasma samples.

6.4.3 Safety Assessments

6.4.3.1 Adverse Events

Adverse events (AEs) will be recorded from the time of consent through the follow-up visit for each subject. AEs may be observed by the site study personnel or spontaneously reported by the subject or reported in response to a standard question from site study personnel and include any protocol-related event.

6.4.3.2 Medical History

A complete medical history will be taken during the Screening Visit and will include evaluation for past and present cardiovascular, respiratory, gastrointestinal, renal, hepatic, neurological, endocrine, lymphatic, hematologic, immunologic, dermatologic, psychiatric, and genitourinary diseases, surgical history, or any other diseases or disorders. Medical events or conditions that arise or worsen in severity or frequency following telavancin administration will be recorded as a (Treatment Emergent Adverse Event) TEAE.

6.4.3.3 Medication History

All medications used within the past 30 days will be recorded.

6.4.3.4 Physical Examination

The physical examination at Screening will be performed by an appropriately qualified individual (e.g., physician or nurse practitioner or physician's assistant or equivalent under the supervision and/or delegation of a physician) and will include examination of the following: general appearance; head, ears, eyes, nose, and throat; neck, skin/dermatologic system; cardiovascular system; respiratory system; abdomen/gastrointestinal system; genitourinary system, lymphatic system; musculoskeletal system; and nervous system. Post screening examinations will be abbreviated and based on symptomatology, largely focused on evaluation of AEs, if any, and any abnormalities identified on the Screening examination.

6.4.3.5 Vital Signs

Heart rate, systolic and diastolic blood pressure, respiratory rate, and body temperature will be taken as outlined in Table 1 and Table 2.

Blood pressure and heart rate will be measured after the subject has been resting for at least 5 minutes in the seated or supine position. Blood pressure will be measured using a calibrated manual or automatic blood pressure device. Heart rate will be recorded by palpation of the radial pulse over a 60-second period or by the automated blood pressure device.

Body temperature will be measured (oral, tympanic, or axillary) using a digital thermometer and recorded in degrees Celsius.

Any screening or pre-dose vital sign outside the normal range may be repeated once at the discretion of the investigator.

6.4.3.6 Electrocardiograms

Twelve-lead ECGs will be collected at each scheduled time point as specified in the Table 1 after the subject has been resting in the supine position for at least 10 minutes. If the screening ECGs are collected less than 24 hours before study drug dosing, the ECG prior to dosing may be omitted.

6.4.3.7 Laboratory Tests

The following laboratory assessments will be performed as specified in Table 1 and Table 2. Refer to the Laboratory Manual for specific information on the collection and processing of laboratory tests.

Additional and repeat laboratory safety testing for the evaluation of abnormal results and/or adverse events during the study may be performed at the discretion of the Investigator or upon request of the Sponsor. Repeat laboratory testing of abnormal potentially clinically significant or clinically significant results for the Screening evaluation of the subject may be repeated once at the discretion of the Investigator.

All laboratory safety testing will be performed by the local laboratory. These local laboratory safety test results will be used to determine a subject's eligibility for entry into the study. Study specific lab results will be entered into the case report form. If standard clinical

laboratory tests have been performed within the protocol-specified windows for laboratory testing at screening or Day 2, the results may be used to avoid excessive blood draws.

6.4.3.7.1 Hematology

Hematology samples will be analyzed for the following: hematocrit and hemoglobin; red blood cell count; white blood cell count, including automatic differential count (percent and absolute) of neutrophils, eosinophils, basophils, monocytes, lymphocytes; mean corpuscular volume; mean corpuscular hemoglobin; mean corpuscular hemoglobin concentration; and platelet count.

6.4.3.7.2 Serum Chemistry

Serum chemistry samples will be analyzed for the following: albumin, sodium, potassium, calcium, chloride, bicarbonate, glucose, BUN, creatinine, total bilirubin, alkaline phosphatase, lactate dehydrogenase, alanine aminotransferase (ALT), aspartate aminotransferase (AST), and gamma-glutamyl transferase.

6.4.3.7.3 Urinalysis

Urinalysis includes determination of pH; specific gravity; presence of blood, glucose, protein, ketones, bilirubin, urobilinogen, nitrite, and leukocytes; and microscopic examination of sediment, if clinically indicated.

6.4.3.7.4 Pregnancy Tests

Serum β -human chorionic gonadotropin pregnancy tests will be performed for all females who are post menarche.

6.5 Safety Data Review Committee

A Safety Data Review Committee (SDRC) will be composed of internal Sponsor personnel only, including the Cumberland Clinical Study Director, the Medical Monitor, the statistician and the PK scientist. Additional members may be added as needed at the discretion of the Clinical Study Director.

An SDRC meeting will be held after the enrollment of approximately every 8 subjects for Cohorts 1-3 and after approximately 6 subjects for Cohort 4. Data from these subjects has to be completed and available before the meeting. The SDRC will also meet if a Stopping Rule is met (Table 4). Available safety data, including demographic data, ECG results, vital

signs, adverse events, and laboratory results, and any available PK data will be reviewed at each meeting. Additional meetings will be scheduled as needed to review safety and available PK data.

As enrollment in Cohorts 1, 2, 3 and 4 may be ongoing during the SDRC, the SDRC may recommend that the study continues without modification; dosing adjustments; a cohort be expanded; or that dosing be discontinued.

Table 4: Stopping Rules

Scenario	Action

Any occurrence of a suspected telavancin-related moderate adverse drug reaction of the same system class (eg, cardiovascular) observed in two or more subjects
 
* Exception: red man syndrome, local site reactions,
	
 • Stop dosing additional subjects and convene SDRC (if event occurs outside the regularly scheduled review). • Review AE and all relevant safety data for evidence of relationship to treatment and clinical or medical significance. • Upon unanimous decision by the SDRC, one of the following decisions may be made: 
 – Discontinue enrollment – Continue enrollment 
** If moderate red man syndrome is observed in at least two subjects, then the rate of telavancin infusion will be decreased by 50% for subsequent subjects


Any occurrence of a suspected telavancin-related severe or serious adverse drug reaction
	
 • Stop dosing additional subjects and convene SDRC (if event occurs outside the regularly scheduled SDRC). • Review AE and all relevant safety data for evidence of relationship to treatment and clinical or medical significance. • If a severe or serious adverse event is determined by the SDRC to be related to study drug and clinically or medically significant, no further administration at this dose should occur. Enrollment of the study may continue at a lower dose upon unanimous decision of the SDRC.

6.6 Concomitant Medications

Concomitant use of other antibiotics for bacterial infections, prophylaxis, or empiric therapy for a suspected bacterial infection are allowed during the study.

Subjects cannot participate in the study if they are:

- Receiving concomitant vancomycin treatment AND require vancomycin drug monitoring levels within 24 hours of receiving the telavancin dose. NOTE: Telavancin might interfere with some Vancomycin therapeutic drug monitoring assays. Caution should be exercised when interpreting vancomycin drug monitoring levels in the presence of telavancin.

- Subject requires, or is anticipated to require, concomitant (within 24 hours before or 24 hours following telavancin administration), administration of agents that are associated with torsade de pointes.

Additional prescription and over-the-counter medications are permitted. Any addition or change in regimen of concomitant medications should be recorded in the source documents and the eCRF. Medications taken from 30 days before enrollment through Follow-Up should be recorded in the source documents and eCRF.

6.7 Discontinuation

6.7.1 Subject Discontinuation

Any subject (or his or her legally authorized representative) may withdraw their consent to participate in the study at any time without prejudice. The investigator must withdraw from the study any subject who requests to be withdrawn. A subject's participation in the study may be discontinued at any time at the discretion of the investigator and in accordance with his or her clinical judgment. When possible, the tests and evaluations listed for the early termination visit should be carried out. If a subject withdraws before completing the study, the reason for withdrawal is to be documented on the CRF.

The Sponsor will be notified of all subject withdrawals.

Reasons for which the investigator or the Sponsor may withdraw a subject from the study or a subject may choose to terminate participation before completion of the study include, but are not limited to, the following:

- Adverse event
- Subject choice
- Major violation of the protocol
- Termination of the study by the Sponsor
- Other

Subjects who discontinue study drug early due to an adverse reaction or any other reason (other than withdrawal of consent) should be encouraged to continue their participation in the follow-up safety assessments. If a subject fails to return for scheduled visits, a documented effort (e.g., at least 2 phone calls to the subject and a certified letter) must be made to determine the reason.

6.7.2 Subject Replacement

Subjects who discontinue the study due to an AE will not be replaced. Subjects with serious protocol violations where PK is not evaluable will be replaced. Subjects discontinued for other reasons may be replaced at the Sponsor's discretion.

6.7.3 Study Discontinuation

The Sponsor reserves the right to discontinue this study at any time for any reason.

6.8 Pregnancy

If a female subject or partner of a male subject becomes pregnant during the study, the Sponsor clinical study director (or designee) must be notified immediately. Follow-up information regarding the outcome of the pregnancy and any postnatal sequelae in the infant will be required.

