1.4.2 Subjects of Childbearing Potential

Adverse developmental outcomes were observed in three animal species at clinically relevant telavancin doses. This raises concerns about potential adverse developmental outcomes in humans (Section 5.4 of VIBATIV® prescribing information). Thus, female subjects who are post menarche are required to have a negative serum pregnancy test before the administration of study drug (Section 4). Females who are post menarche should be apprised of the animal teratology findings observed with the administration of telavancin. Males should be apprised of the effects on sperm count, motility, and morphology that were noted in animals exposed to telavancin.

Females of childbearing potential (defined as females who are post menarche) and sexually active males participating in telavancin studies must agree to use appropriate contraceptive measures for at least 30 days after the single dose of telavancin. Medically acceptable contraceptives include surgical sterilization; approved hormonal contraceptives (i.e., birth control pills, Depo-Provera®, or Lupron Depot®); barrier methods (i.e., condom, diaphragm) used with a spermicide; or an intrauterine device. Abstinence is a valid form of contraception. Study participants should be advised to inform the study physician immediately if they become pregnant, or their partner becomes pregnant, while participating in the study.

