7.4 Serious Adverse Events

A serious adverse event (SAE) is defined as any adverse drug experience occurring at any dose that results in any of the following outcomes:

- Death
 - Life-threatening situation (subject is at immediate risk of death)
-

- Inpatient hospitalization or prolongation of existing hospitalization (excluding those for study therapy or placement of an indwelling catheter, unless associated with other serious events)
- Congenital anomaly/birth defect in the offspring of a subject who received study drug
- Other: Important medical events that may not result in death, be immediately life-threatening, or require hospitalization, may be considered an SAE when, based upon appropriate medical judgment, they may jeopardize the subject and may require medical or surgical intervention to prevent one of the outcomes listed in this definition. Examples of such events are as follows:
 - Intensive treatment in an emergency room or at home for allergic bronchospasm
 - Blood dyscrasias or convulsions that do not result in hospitalization
 - Development of drug dependency or drug abuse

Additional Considerations for Serious Adverse Events

- Death is an outcome of an adverse event and not an adverse event in itself. In reports of death due to disease progression, where no other information is provided, the death will be assumed to have resulted from progression of the disease being treated with the study drug(s).
- All deaths, regardless of cause, must be reported for subjects if the death occurs while the subject is participating in the study.
- “Occurring at any dose” does not imply that the subject is receiving study drug at the time of the event; dosing may have been given as treatment cycles or interrupted temporarily before the onset of the SAE, but may have contributed to the event.
- “Life-threatening” means that the subject was at immediate risk of death from the event as it occurred. This does not include an event that might have led to death, if it had occurred with greater severity.
- Complications that occur during hospitalizations are AEs. If a complication prolongs hospitalization, it is an SAE.
- “Inpatient hospitalization” means the subject has been formally admitted to a hospital for medical reasons, for any length of time. This may or may not be overnight. It does not include presentation and care within an emergency department.

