7.6 Serious Adverse Event Reporting

Any SAE that occurs after a subject signs an informed consent form through the follow-up visit (or at the time a subject is determined to be ineligible for the study or who does not enroll in the study), regardless of causal relationship, must be reported to the Sponsor within 24 hours of the investigator's knowledge of the event.

To report an SAE, complete and fax the Serious Adverse Event Report Form to the following:

[REDACTED]

For medical questions regarding an SAE, contact the Sponsor medical monitor by telephone as follows:

[REDACTED]

For fatal or life-threatening events, also fax copies of hospital case reports, autopsy reports, and other documents when requested. Additional information may be requested from the investigator to ensure the timely completion of accurate safety reports.

An SAE may qualify for reporting to regulatory authorities if the SAE is possibly attributable to the study drug and is unexpected/unlisted based on the current Telavancin Investigator's Brochure. In this case, all investigators will receive notification of the event. The investigator is responsible for notifying the Institutional Review Board or Ethics Committee and documenting the notification, as required by local regulatory authorities and in accordance with the local institutional policy.

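### The pregnancy reporting trigger ends about 7 days after the dose, while the protocol requires contraception for 30 days, so 22 to 24 of those days carry no reporting duty

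*Combined protocol and SAP*

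**What the plan says.** **Reason for caution.** Section 1.4.2 reports adverse developmental outcomes in three animal species at clinically relevant doses, and effects on sperm in exposed animals. It then says that post-menarche females and sexually active males "must agree to use appropriate contraceptive measures for at least 30 days after the single dose of telavancin". Inclusion criterion 4 (Section 4.1) also sets 30 days after the dose, in addition to the study period.

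**Pregnancy reporting.** Section 6.8 makes notification of the sponsor conditional: "If a female subject or partner of a male subject becomes pregnant during the study". Sections 1.4.2 and 6.3.6 advise participants to tell the study physician "if they become pregnant, or their partner becomes pregnant, while participating in the study". Section 1.4.2 therefore holds both the 30-day contraception period and the shorter reporting duty. For a pregnancy that has been notified, Section 6.8 adds: "Follow-up information regarding the outcome of the pregnancy and any postnatal sequelae in the infant will be required". It gives no end date.

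**End of participation.** Section 3.1 has subjects complete the study after the Day 8 ± 1 evaluation, which Section 6.3.4 places 7 days after dosing and allows to be a telephone call. Section 6.3.5 states: "Study termination will be considered the date that the subject withdraws from or completes the study". The synopsis gives a participation of up to 9 days.

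**Serious adverse events.** Section 7.4 lists "Congenital anomaly/birth defect in the offspring of a subject who received study drug" among the criteria for a serious adverse event. Section 7.6 requires reporting within 24 hours for "Any SAE that occurs after a subject signs an informed consent form through the follow-up visit".

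**The concern.** The sponsor thought the reproductive findings serious enough to require contraception for 30 days after a single dose. If contraception fails within that period, one would expect the protocol to ask to be told. As written, it asks only about pregnancies that begin by about Day 8. A participant, or a participant's partner, who conceives two or three weeks after the dose is still inside the contraception period but has no stated duty to report. Outcome follow-up under Section 6.8 then never starts.

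The serious-adverse-event rules have a related mismatch. A congenital anomaly in offspring is named as a criterion, but a birth defect from a pregnancy that begins in this study would be found long after the reporting window has closed.

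What is at stake is safety information on any exposed pregnancy. The pharmacokinetic objective is not involved.

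**Working it through.** **1. The plan's own duration.** Inputs: screening within 48 hours before dosing (Section 6.3.1), follow-up 7 days after dosing with a tolerance of ±1 day (Section 6.3.4).

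- Screening plus follow-up: 2 + 7 = 9 days, which reproduces the synopsis figure. Counting study days from Day 1 to Day 8 + 1 also gives 9.
- With the full screening window and the extra day together, elapsed time is 2 + 8 = 10 days. The difference does not matter here.

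**2. Days of the contraception period covered by the trigger.** Dosing is on Day 1, so Day 8 ± 1 is 6 to 8 days after the dose. Share covered = (days from dose to follow-up) / 30.

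| Follow-up, days after dose | Share covered | Days not covered | Share not covered |
|---|---|---|---|
| 6 | 6/30 = 20% | 24 | 80% |
| 7 | 7/30 = 23% | 23 | 77% |
| 8 | 8/30 = 27% | 22 | 73% |

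**3. Does another section bridge the gap?** Section 7.7 continues follow-up of an adverse event that a subject is already experiencing; it creates no duty to report something new after the follow-up visit. Section 7.6 closes at that visit. Section 6.8 has no end date for outcomes, but it applies only after its trigger has been met. None of these reaches a conception after about Day 8.

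**4. Birth defects.** For a notified pregnancy, Section 6.8 collects the outcome and infant sequelae, so an anomaly can reach the sponsor by that route. What is missing is the 24-hour duty under Section 7.6, although Section 7.4 classes the event as serious.

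**5. Recognition.** The only scheduled pregnancy test is at screening (Table 1, Section 6.3.1), and the follow-up contact lists only adverse events and concomitant medications. The documents give no delay from conception to recognition. Assume 7 to 28 days, with conception uniform over the 30 days.

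- Share of the 30 days both conceived and recognised before participation ends = max(0, follow-up day − delay) / 30. With follow-up at 7 days this is 0% for every delay in the range. The maximum is (8 − 7)/30 = 3%.
- If reporting were simply extended to close on day 30, the share recognised by then would be (30 − delay)/30: 77%, 67%, 53%, 30% and 7% for delays of 7, 10, 14, 21 and 28 days.

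A rule that counts by date of conception, whenever recognised, covers the whole 30 days. A calendar cut-off does not.

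**The case against.** **Exposure is short.** At the adult half-life of 8.1 hours (Section 3.2), five half-lives are 5 × 8.1 = 40.5 hours, and 0.5^(48/8.1) ≈ 1.6% of drug remains at 48 hours (single-exponential approximation, with the paediatric half-life assumed similar). Conceptions with meaningful plasma exposure therefore fall within participation. This stands as pharmacology and lowers the stakes. It does not remove the mismatch: the sponsor chose 30 days despite that half-life, and the animal sperm effects in Section 1.4.2 may not follow plasma concentration.

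**Few pregnancies are expected.** If all 8 adolescents were at risk at the 1% per year ceiling for contraceptive failure in Section 4.1, the uncovered days would yield 8 × 0.01 × 23/365 ≈ 0.005 pregnancies; a tenfold higher rate gives about 0.05. This also stands. The study cannot estimate a reproductive risk under any wording, and an absence of reports would be uninformative either way. The case for the change rests on the value of an individual report and on internal consistency.

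**Birth defects are not lost altogether.** A reader might infer that they cannot be captured at all. Section 6.8 contradicts that for any notified pregnancy.

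**Consent forms.** Consent pages are not in the available text, so what subjects are told there about later pregnancies cannot be judged.

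**Conclusion.** The mismatch is real and should be corrected, although its practical scale is small. By date of conception, the reporting trigger covers 20–27% of the protocol's own 30-day contraception period and leaves 22 to 24 days (73–80%) without a reporting duty. Separately, a congenital anomaly has no route through the Section 7.6 window, although Section 6.8 can still collect it once the pregnancy has been notified. The day count rests only on the plan's dates and on reading participation as ending at the Day 8 ± 1 contact.

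Two stronger readings are not supported. One is that the rule captures almost no pregnancies. That needs a requirement that the pregnancy be recognised before Day 8; Section 6.8 turns on when the pregnancy begins and says nothing about when it must be recognised. The other is that the protocol defines a 30-day period of fetal risk. It states a contraception period; how long risk lasts is an inference from it.

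Those affected are post-menarche females and partners of post-pubertal males: mainly Cohort 1, with possibly a few subjects aged 6 to 11.

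**What to change.** - **Sections 1.4.2, 6.3.6 and 6.8:** require reporting of any pregnancy in a subject or partner that is present at dosing, including one too early for the screening test to detect, or that is conceived from consent through 30 days after the dose, whenever it is recognised. The window should not start at dosing: screening can precede dosing by 48 hours, and a conception in that interval would be present when drug is given. The present wording, which turns on becoming pregnant during the study, may also literally exclude a conception before consent.
- **Section 7.6:** exempt congenital anomalies arising from these pregnancies from the follow-up-visit cut-off.
- **Section 6.3.4:** add a reminder of the continuing reporting duty to the existing Day 8 visit or call.

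The cost is an amendment and matching consent wording, with no added visit or test. The downsides are that the sponsor's safety reporting stays open longer for a few subjects, and that capture after Day 8 still relies on self-report.
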